3.7.2 Secondary outcome

The secondary outcome will be assessed by measuring 25(OH)D serum levels. Correlations will be assessed between participants' 25(OH)D levels at enrolment, changes in 25(OH)D levels from enrolment to 3 months, and 25(OH)D levels at 3 months and fracture healing as described above.

3.7.3 Other secondary outcomes

The other secondary outcomes will include assessing supplementation adherence between daily and loading doses, confirming participant safety as measured by AEs and serum levels of calcium and parathyroid hormone (PTH), and assessing protocol adherence (e.g. completion of outcome assessment and participant follow-up).

Adherence with vitamin D supplementation will be assessed by participant self-report, by counting the tablets for the daily doses at each follow-up, and by direct observation for the loading doses.

Participant safety will be assessed by AEs, defined as any symptom, sign, illness, or experience that develops or worsens in severity during the course of this study. Within the AEs collected, fracture healing complications will be identified, and will include nonunion (defined as failure of the fracture to progress towards healing for 2 consecutive months and at least 6 months post-fracture), delayed union (defined as a failure of progression of fracture healing beyond the expected median healing time of 4 months with pain at the fracture site), hardware failure (defined as broken or bent nail or locking screw),³³ wound healing problems (previously published criteria by Anglen 2005), and infection (superficial and deep as defined by Centers for Disease Control and Prevention (CDC) criteria). Wound healing problems and infection are a part of the composite fracture healing complication outcome because previous animal and infectious disease clinical research has suggested that vitamin D can improve wound healing and reduce infections.³⁴⁻³⁷ In addition to AEs, serum levels of calcium and PTH will be monitored and we will record results of the participants' pre-operative metabolic profile. These data will be used to understand the baseline metabolic health of the participants and will be used as needed in the event of suspected AEs.

Participant adherence with the protocol will be assessed by monitoring the completion of outcome measures, including clinic assessments (FIX-IT), radiographs (RUST), and blood work (CTX, PINP, 25(OH)D, calcium, and PTH), documentation of AEs and re-operations, and completion of follow-up to 12 months.

3.7.4 Data collection and participant follow-up

Upon providing informed consent, baseline demographics will be collected from the patient and from their medical chart (**Table 1**). This includes demographic, medical history, pre-operative blood work-up details (e.g. kidney and liver function tests, calcium, phosphate, and albumin), injury details, fracture characteristics, details on the surgical management of their fracture, and rehabilitation details. Participants will have blood drawn within the fracture clinic that will be analyzed for calcium levels and for CTX, PINP, 25(OH)D, and

PTH (See Section 3.7.5). Post-operative x-rays will be taken as per standard of care (See Section 3.7.6).

Participants will be followed at standard clinical visit intervals for 12 months post-injury including 6 weeks, 3 months, 6 months, 9 months, and 12 months. The Schedule of Events (**Table 1**) details the requirements and procedures for each visit. Participants will have blood drawn within the fracture clinic that will be analyzed for calcium, CTX, PINP, 25(OH)D, and PTH serum levels at 6 weeks and 3 months (See Section 3.7.5). Post-operative x-rays will be taken as per standard of care at each follow-up visit (See Section 3.7.6). Participants will be assessed clinically for FIX-IT at each visit. All study outcomes (as defined above) will be documented on the case report forms (CRFs) at each follow-up visit. A 12-month follow-up was selected because is a standard follow-up period for patients with tibial and femoral shaft fractures and it is a commonly used follow-up period for similar fracture trials.^{7,38} In addition, it is a commonly referenced time period for fracture healing complications requiring reoperation, and will further inform decisions surrounding the larger, definitive phase III RCT.

3.7.5 Analysis of blood samples

Serum calcium testing will be performed by the hospital laboratory and will be part of the unblinded medical chart for patient safety. The remainder of serum samples (PTH, 25(OH)D, PINP, CTX) will be analyzed in a blinded manner at the end of the study. Laboratory personnel at the University of Maryland's Muscle Research Laboratory will process the samples for storage in the -80° C freezer. Upon completion of all blood work for the study, the serum samples will be transferred to the Institute for Clinical and Translational Research Clinical Research Unit Core Laboratory to be analyzed as a single batch to eliminate inter-batch assay variability. The results of the analyses will be sent to the CEO to be added to the REDCap study database and included within the final data analysis. The treating surgeon will remain blinded to these results. Participants may request the results of their blood analysis at the end of the study.

3.7.6 Analysis of radiographs

The radiographs will be stored in the STC Picture Archiving and Communication System (PACS) at the STC and then sent to the CEO for the review of radiographic fracture healing (RUST) by an independent practicing orthopaedic surgeon.

3.8 Participant Retention

Once a participant is enrolled in the trial, every reasonable effort will be made to follow the participant for the entire duration of the study period. The expected follow-up rate for this study is greater than 90% based on similar fracture trials.^{7,38-40} To maximize participant retention, all possible attempts should be made to collect as much data as possible and to reduce loss to follow-up. We have implemented procedures to improve participant retention (**Figure 4**).⁴¹

We will only deem participants lost to follow-up after all exhaustive measures have been taken to locate the participant. Participants should not be deemed lost to follow-up until the 12-month visit is due and all attempts to contact the participant have been exhausted.

We will not remove participants from the study if the study protocol was not adhered to (e.g. participant received wrong treatment arm, early discontinuation of supplements, occurrence of protocol deviations, missed follow-up visits, etc.). We will document the reasons for participant withdrawal from the trial (e.g. withdrawal of consent or lost to follow-up).

4.0 STATISTICAL PLAN

4.1 Sample Size Determination

This trial will use a phase II randomized screening design to facilitate non-definitive comparisons of three vitamin D₃ dosing regimens. Using the principles outlined by Rubinstein et al, the statistical parameters have been carefully chosen to ensure a reasonable sample size and meaningful results.⁴² Consistent with previous recommendations, an α and β of 0.20 was chosen with a target mean difference of 17-20%, depending on the fracture healing measure. There will be no adjustments for multiple testing given the exploratory nature of the study design.

Based on the original instrument development and validation in tibia and femur fracture patients, it is expected that the low dose and control groups will have a mean 3-month FIX-IT score of 8 (standard deviation (SD) 3).¹⁸ Assuming the high dose groups will achieve a mean 2 point increase (17% mean difference), 21 patients are required in each group. The same sample size requirements will be applied for comparisons using the RUST instrument based on similar assumptions and recent literature (2 point mean difference, 8 vs. 6, SD 3).¹⁹⁻²² Clinically important changes in the PINP and CTX markers are unknown; however, in a previous study of tibia fracture healing, Veitch et al observed concentrations of both bone turnover markers approximately 100% greater than baseline values.⁴³ Given the large changes observed in these bone turnover markers, the same criteria will be applied for identifying a potentially clinically beneficial regimen and remain powered to detect a mean difference of 20% (SD 30%). Finally, the sample size will be increased to account for a 10% loss to follow-up, for a total enrolment of 24 patients per allocation group (96 total).

4.2 Statistical Methods

All outcome analyses will be exploratory and adhere to the intention-to-treat principle. As treated sensitivity analyses will also be conducted.

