4.2.1 Specific Aim

Each measure of fracture healing will be described with its mean and SD. For our primary analysis, comparisons for the 3 hypotheses (Section 2.4) will be made using an independent t-test and significance set at $\alpha=0.20$ (**Table 2**). Hypothesis 1 compares high dose supplementation versus low dose. To test this hypothesis, we will combine the two high dose groups (loading and daily) for a 2:1 comparison against the low daily dose group. All other comparisons will be 1:1 based on the treatment groups outlined.

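### The primary t-tests drop anyone without a 3-month value; a repeated-measures model using the 6-week healing data is a cheap improvement

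*Combined protocol and SAP*

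**What the plan says.** Section 4.2 sets the principle: "All outcome analyses will be exploratory and adhere to the intention-to-treat principle". Section 4.2.1 sets the method: "comparisons for the 3 hypotheses (Section 2.4) will be made using an independent t-test", at alpha 0.20. Table 2 repeats it for FIX-IT, RUST, PINP and CTX, and Section 3.7.1 makes 3 months the primary time point.

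On participants who depart from the plan, Section 3.8 says "We will not remove participants from the study if the study protocol was not adhered to", and its examples include stopping supplements early and missing visits. Section 4.1 provides for loss only through numbers: "the sample size will be increased to account for a 10% loss to follow-up", which takes 21 needed per group to 24 enrolled.

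No section gives imputation, a repeated-measures model or a missing-data sensitivity analysis, or says who enters a test when the 3-month value is absent. The one sensitivity analysis (4.2.4, as treated) removes further participants.

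Table 1 schedules FIX-IT, RUST, CTX and PINP at 6 weeks as well as 3 months, and CTX and PINP also at enrolment. Sections 3.7.3 and 4.2.3 plan counts and proportions for completion of the assessments, and Section 3.8 records reasons for withdrawal.

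**The concern.** A t-test of 3-month values can use only people who have one. The 21-to-24 inflation fits that reading, since it assumes that lost participants do not contribute. For anyone who misses the 3-month visit, radiograph or blood draw, the intention-to-treat statement has no method behind it.

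Attendance after trauma may well relate to recovery. Some people may skip clinic because they feel well, others because they are doing badly. If absence depends on early healing and does so differently by arm, the comparison of attenders is biased, in either direction. The 6-week score holds information about the absent participants, and the t-test ignores it. With about 21 analysed per arm, a few selective absences can matter, and the results are meant to inform the Phase III design, including its control group (3.5.2).

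The 10% allowance is also for loss to follow-up, which Section 3.8 does not declare until the 12-month visit is due. Missing 3-month values are a separate quantity and could exceed it.

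**Working it through.** **The plan's own figure.** Inputs from Section 4.1: "an α and β of 0.20 was chosen with a target mean difference of 17-20%, depending on the fracture healing measure"; FIX-IT mean 8, SD 3, difference 2; and "Assuming the high dose groups will achieve a mean 2 point increase (17% mean difference), 21 patients are required in each group".

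- n per group = 2 (z₀.₉₀ + z₀.₈₀)² SD²/Δ² = 2 × (1.2816 + 0.8416)² × 9/4 = 20.3, so 21 (two-sided; one-sided would give 13).
- 21/0.90 = 23.3, so 24; 4 × 24 = 96.
- Exact t-test power at 21 per group is 80.4%.

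The stated 21, 24 and 96 reproduce.

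**Precision under random loss.** If everyone missing at 3 months was seen at 6 weeks, the likelihood estimate of an arm's 3-month mean has variance SD² [(1 − ρ²)/n₃ₘ + ρ²/n₆w]. The documents give no 6-week to 3-month correlation ρ, so it is assumed. Powers below use the normal approximation.

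- 10% missing (21.6 of 24): effective n is 21.8 at ρ = 0.3 and 22.7 at ρ = 0.7. Power is 81.8% for the t-test and 82.1% to 83.3% with the 6-week data.
- 20% missing: 78.3% against 78.9% to 81.4%.
- Three lost at random per arm, ρ = 0.6: the standard error goes from 3√(2/21) = 0.93 to 3√[2(0.64/21 + 0.36/24)] = 0.90 (simulated: 0.93 to 0.91).

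The gain in precision is negligible at the planned loss.

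**Bias by hand.** If m of 24 in an arm leave and their 6-week scores average 1 SD below the arm mean, those who remain average m/(24 − m) SD above it. Their 3-month mean shifts by ρ × SD times that amount.

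- Four poor early healers lost from control, one from active: shift in the difference = −(4/20 − 1/23) × 3ρ = −0.1565 × 3ρ. This is −0.28 at ρ = 0.6 and −0.14 at ρ = 0.3, so estimates of 1.72 and 1.86.
- Three poor early healers lost from control, three good ones from active: −(3/21 + 3/21) × 3ρ = −0.2857 × 3ρ. This is −0.51 and −0.26, so 1.49 and 1.74.
- Three poor early healers lost from each arm: the shifts cancel and the estimate is 2.00.

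**Simulation.** 24 per arm, SD 3, true difference 2, and probability of leaving proportional to exp(±slope × standardised 6-week score). Both the slope and ρ are assumptions. At slope 1.5, someone 1 SD below the mean is e³ ≈ 20 times as likely to leave as someone 1 SD above; at slope 0.5, e¹ ≈ 2.7 times.

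| Loss pattern | t-test, slope 1.5, ρ 0.6 | t-test, slope 0.5, ρ 0.3 | Using 6-week value |
|---|---|---|---|
| Same pattern in both arms (3 and 3) | about 2.0 | about 2.0 | about 2.0 |
| 4 poor healers from control, 1 from active | 1.74 | 1.95 | about 2.0 |
| 3 poor from control, 3 good from active | 1.45 | 1.86 | about 2.0 |

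Random loss of three per arm also leaves both methods near 2.0. At the steep slope and ρ = 0.6, t-test power is about 73% in the second row and 62% in the third, against the planned 80%.

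**Bias the other way.** With no true effect, 10% random loss in one arm, and 21% concentrated in poor early healers in the other, the t-test is biased by 0.17 to 0.37 points (ρ 0.3 to 0.7). It then rejects 20% to 24% of the time at a nominal 20%. The likelihood estimate has bias near 0 and rejects 19% to 20% of the time.

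**The case against.** The best defence is that the bias needs more than outcome-related loss; it needs loss that differs by arm. Allocation is blinded with identical capsules (3.5.1), so poor healers leaving one arm while good healers leave another has no obvious mechanism. The steep slope is also strong, and the correlation is unknown. For FIX-IT it may be low, because the score measures weight-bearing and pain (3.7.1), while Section 3.6.2 permits protected weight-bearing for up to 6 weeks. All of this stands, and it is why the size is given as a range that starts at no bias.

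A reader might infer that the plan abandons intention-to-treat, or discards everyone who discontinues. The documents do not support that. Stopping capsules is not the same as lacking a 3-month value, and those who stop but attend are analysed as randomised. A reader might also infer that the 6-week data are ignored altogether. They may be described with means and SDs under 4.2.1; they are absent only from the comparisons.

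The plan also expects more than 90% follow-up, lists retention measures, and already counts completed assessments. The trial is exploratory, and a t-test is a reasonable tool for that purpose. These points lower the urgency but do not say how a missing 3-month value is handled.

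**Conclusion.** This is a cheap improvement. The gap is definite: the primary test has no provision for a missing 3-month value, and 6-week measurements that bear on it are not used. The consequence is conditional. Against a true difference of 2 FIX-IT points, the t-test has no material bias if loss is random or alike across arms. It understates the difference by 0.05 to 0.26 points in the four-versus-one case, and by 0.14 to 0.55 in the opposite-pattern case. These figures rest on assumed correlations of 0.3 to 0.6, assumed slopes, and every leaver having been seen at 6 weeks.

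The documents do not show that the trial's result will be biased, and they do not show a faulty sample size.

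**What to change.** In Section 4.2.1 and Table 2, take the same three 3-month contrasts at alpha 0.20 from a likelihood-based repeated-measures model for each measure. Include arm, visit (6 weeks, 3 months) and arm-by-visit, plus the enrolment value for CTX and PINP. Include every randomised participant with at least one post-baseline value. For Hypothesis 1, the contrast is the average of the two high-dose arms against the low-dose arm. Keep the t-test as a supportive analysis. Break the already planned completion counts and withdrawal reasons down by arm for each 3-month measure.

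The cost is plan wording and slightly more analysis work, with no new visits or data. The limits are these:

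- The model assumes that missingness is explained by observed values.
- It does nothing for FIX-IT or RUST in participants lost before 6 weeks, because neither has an enrolment score.
- It gains less for FIX-IT if 6-week scores mainly reflect permitted weight-bearing restriction.

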4.2.1 Specific Aim

Each measure of fracture healing will be described with its mean and SD. For our primary analysis, comparisons for the 3 hypotheses (Section 2.4) will be made using an independent t-test and significance set at $\alpha=0.20$ (**Table 2**). Hypothesis 1 compares high dose supplementation versus low dose. To test this hypothesis, we will combine the two high dose groups (loading and daily) for a 2:1 comparison against the low daily dose group. All other comparisons will be 1:1 based on the treatment groups outlined.

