3.2 Eligibility Criteria

The inclusion criteria are: 1) adult men or women ages 18-50 years; 2) closed or low grade open (Gustilo type I or II) tibial or femoral shaft fracture;²⁴ 3) fracture treated with a reamed, locked, intramedullary nail; 4) acute fracture (enrolled within 7 days of injury); and 5) provision of informed consent. Fifty years was selected as the upper age limit to minimize potential confounding with post-menopausal endocrine changes that affect bone metabolism. For the purposes of the study, femoral shaft fractures will be defined as any injury in which the majority of fracture line is distal to the lesser trochanter and proximal to the distal metaphyseal flare of the femoral condyles (**Figure 1**). Intertrochanteric extension or distal articular extension is permitted. Similarly, a tibial shaft fracture will be defined as an injury with a primary fracture line between the proximal meta-diaphyseal flare to the distal metaphyseal region ending one joint width proximal to the tibial plafond (**Figure 2**). Intra-articular extension is permitted.

The exclusion criteria are: 1) osteoporosis; 2) stress fractures; 3) elevated serum calcium (>10.5 mg/dL); 4) atypical femur fractures as defined by American Society for Bone and Mineral Research (ASBMR) criteria;²⁵ 5) pathological fractures secondary to neoplasm or other bone lesion; 6) patients with known or likely undiagnosed disorders of bone metabolism such as Paget's disease, osteomalacia, osteopetrosis, osteogenesis imperfecta etc.; 7) patients with hyperhomocysteinemia; 8) patients with an allergy to vitamin D or another contraindication to being prescribed vitamin D; 9) patients currently taking an over the counter multivitamin that contains vitamin D and are unable or unwilling to discontinue its use for this study; 10) patients who will likely have problems, in the judgment of the investigators, with maintaining follow-up; 11) pregnancy; 12) patients who are incarcerated; 13) patients who are not expected to survive their injuries; and 14) other lower extremity injuries that prevent bilateral full weight-bearing by 6 weeks post-fracture.

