3.4 Randomization Methods

Each participant will be randomized to 1 of 4 treatment groups: 1) 150,000 IU loading dose vitamin D₃ plus daily dose placebo; 2) loading dose placebo plus 4,000 IU vitamin D₃ per day; 3) loading dose placebo plus 600 IU vitamin D₃ per day; or 4) loading dose placebo plus daily dose placebo. The daily vitamin D₃ supplements/placebo will be provided in a blinded manner. The daily treatment will commence within 1 week of injury and will be taken for 3 months. The loading dose vitamin D₃ supplements/placebo will be given within 1 week of injury and at 6 weeks (+/- 2 weeks) post-injury.

Allocation to the 4 study groups will be concealed using a centralized 24-hour computerized randomization system that will allow internet-based allocation. The treatment allocation will be stratified on the following prognostic factors to ensure balance between the intervention groups: fracture type (closed vs. open) and long bone fracture (tibia vs. femur).

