3.7 Primary and Secondary Outcome Measures

3.7.1 Primary outcome

Fracture healing will be assessed as follows: 1) clinical fracture healing will be measured using FIX-IT, 2) radiographic fracture healing will be measured using the RUST, and 3) biological fracture healing will be measured using serum levels of CTX and PINP.

Clinical Healing: FIX-IT is a standardized measure of weight-bearing and pain in patients with lower extremity fractures, specifically tibia and femur fractures.¹⁸ Preliminary validation of the FIX-IT has demonstrated high inter-rater agreement and moderate correlation with the physical scores of the Short Form-36.¹⁸ It has been used in other studies to assess clinical fracture healing.

Radiographic Healing: The RUST score assesses the presence of bridging callus or a persistent fracture line on each of 4 cortices.¹⁹⁻²² This score has been previously validated and found to have greater inter-rater reliability when compared with surgeons' general impression of the cortical bridging.¹⁹⁻²² RUST has been widely used to assess radiographic fracture healing.¹⁹⁻²² An orthopaedic surgeon who is independent of the study will review the images and assign a RUST score.

Biological Healing: CTX is a bone-resorption marker and previous research has found that it rises 1 week after fracture of the tibial shaft and remains elevated throughout fracture healing.²³ PINP is a bone-formation marker and prior research has found that it is highest at 12 weeks after fractures of the tibial shaft and proximal femur.³²

The primary time point for assessing fracture healing will be at 3 months post-injury. This time point was selected because it coincides within the standard clinical follow-up schedule, and because it has the greatest potential to detect differences in short-term fracture healing. While we expect the 1-year fracture union rate to be approximately 95% for the femur fractures³² and 75% for the tibia fractures (unpublished data from the SPRINT trial),⁷ improved early fracture healing is biologically plausible. The median time to fracture union for tibia fractures is 4 months; therefore, many patients are still experiencing morbidity from their injury at the 3-month visit and decreasing the time to union would be an important patient benefit.

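### The primary t-tests leave the two stratification factors, and possibly baseline CTX and PINP, unused; a prespecified adjusted model is a cheap efficiency gain, not the repair of an error

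*Combined protocol and SAP*

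**What the plan says.** Section 4.2.1 states that "comparisons for the 3 hypotheses (Section 2.4) will be made using an independent t-test and significance set at" 0.20. Table 2 repeats this for each of the three hypotheses and each of the four measures. H1 pools the two high-dose arms against low dose (2:1). H2 (loading against high daily) and H3 (low dose against placebo) are 1:1. Section 4.2.4 only repeats the analyses as treated. No section adjusts the primary comparisons.

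Section 3.4 says: "The treatment allocation will be stratified on the following prognostic factors to ensure balance between the intervention groups", and names them as "fracture type (closed vs. open) and long bone fracture (tibia vs. femur"). It gives no blocking method.

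In Section 3.7.1, "biological fracture healing will be measured using serum levels of CTX and PINP", and "The primary time point for assessing fracture healing will be at 3 months post-injury". Table 1 schedules CTX and PINP at Visit 1, 6 weeks and 3 months. It schedules FIX-IT and RUST only from 6 weeks, so those two measures have no baseline and can be adjusted for the strata only.

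**The concern.** The plan names two factors as prognostic and builds the allocation around them, then leaves them out of the analysis. It also draws baseline blood for two of the four measures and, if the outcome is the 3-month level, does not use it.

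Two things follow to the extent that these variables predict outcome:

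- **Power.** Outcome variance that a covariate could remove stays in the error term.
- **Size.** If allocation is balanced within strata, the t-test's standard error still contains between-stratum variance that balance has removed from the treatment difference. The true type I error then falls below the declared 0.20. For a screening trial that chose a liberal alpha on purpose, this gives back part of that choice. Leaving out the baseline marker costs power only, because allocation is not balanced on it.

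**Working it through.** **1. The plan's own figure.** Section 4.1 gives a difference of 2 with SD 3, or for the markers a 20% difference with SD 30%. Either way d = 0.667. With alpha and beta both 0.20, two-sided:

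n = 2(1.2816 + 0.8416)² / 0.667² = 2 × 4.508 / 0.444 = 20.3, so 21 per group.

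A one-sided test would need 13, so the plan is two-sided. Allowing for 10% loss, 21/0.9 = 23.3, so 24 per group and 96 in total. This reproduces. Noncentral-t power is 80.4% for 21 against 21 and 88.4% for H1 (42 against 21).

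**2. A reference value for the strata.** No document gives an R² for any primary measure. The nearest figure is 1-year union: "While we expect the 1-year fracture union rate to be approximately 95% for the femur fractures" and 75% for the tibia. With femur share w and p = 0.95w + 0.75(1 - w), the share of variance explained by bone is

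R² = w(1 - w) × 0.20² / [p(1 - p)].

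This gives 0.055 at w = 0.30, 0.078 at w = 0.50, and at most 0.086 near w = 0.67. It is a different outcome at a different time, so it serves only as a reference point.

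**3. Adjusting for the strata.** The model was simulated with four arms, bone and fracture type: 96 randomised, 84 analysed (4 × 21). Assumed: 50% tibia, 25% open, three quarters of R² from bone, 6,000 runs, Monte Carlo error about 0.5 point. Ranges cover blocks of 4 and 8, also assumed.

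| Strata R² | t-test size, blocked | 1:1 power, t-test → model | H1 power, t-test → model |
|---|---|---|---|
| 0 | 0.198–0.203 | 79.7–81.1 → 80.0–81.2% | 88.1–88.2 → 88.0–88.2% |
| 0.05 | 0.188–0.202 | 80.4–80.9 → 81.6–81.7% | 88.7 → 89.0–89.4% |
| 0.086 | 0.182–0.185 | 80.8–81.3 → 83.0–83.3% | 88.9–89.0 → 90.2–90.3% |
| 0.20 | 0.156 | 81.8–82.3 → 86.4–86.7% | 89.9–91.0 → 92.5–93.9% |

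The gain at R² 0.086 is about 2 points (1:1) and 1.3 points (H1). At 0.20 it is about 4.5 and 2.8 points. Large-sample check of size under perfect balance, 2[1 - Φ(1.2816/√(1 - R²))]: 0.180 at 0.086 and 0.152 at 0.20.

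With simple randomisation within strata, t-test size stays at about 0.20, and 1:1 power goes from 80.3 to 82.0% at R² 0.086 and from 79.1 to 85.5% at 0.20.

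**4. Adding the baseline marker (outcome taken as the 3-month level).** The residual SD is 30% × √(1 - ρ²), and residual degrees of freedom are 84 - 4 - 3 = 77. Simulation used blocks of 4, strata R² 0 and 7,000 runs.

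| Assumed ρ | 1:1 model power, simulated | analytic |
|---|---|---|
| 0 | 79.6% | 80.7% |
| 0.2 | 81.0% | 81.9% |
| 0.3 | 82.4% | 83.4% |
| 0.5 | 88.6% | 88.5% |
| 0.7 | 95.0% | 95.8% |

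The t-test stays at about 80% power and 0.20 size throughout. The correlation may be low, because the first sample is taken after injury: "acute fracture (enrolled within 7 days of injury").

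**5. Cost if the covariates are useless.** Mean change in power against the t-test, in points, from exact design matrices of the four-arm model:

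| Model | Comparison | Blocks of 4 | Blocks of 8 | Simple within strata |
|---|---|---|---|---|
| Strata only | 1:1 | +0.2 | +0.15 | -0.4 |
| Strata only | H1 | -0.1 | -0.1 | -0.7 |
| Strata and baseline | 1:1 | -0.2 | -0.2 | -0.8 |
| Strata and baseline | H1 | -0.4 | -0.4 | -1.05 |

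These are averages. With baseline included, the 5th percentile across trials is about -1.3 with blocks and about -2.7 with simple randomisation. Pooling variance over four arms contributes about +0.3 point for 1:1 comparisons (80.75% against 80.44%) and requires similar SDs.

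**6. Missing baselines.** If the marker model simply drops such patients, then at ρ = 0 one per arm takes power from 80.4% to about 79.3%, and two per arm to about 77.7%. At ρ = 0.2, one per arm leaves about 80.5%, so the gain is gone.

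**The case against.** The strongest reply is that nothing here is wrong. The t-test is valid, the sample size is right, and Sections 4.1 and 4.2 call the comparisons non-definitive and exploratory. At the only R² linked to the documents, FIX-IT and RUST gain about 2 points. All of this stands, and it limits the point to an efficiency gain.

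Four more specific objections also have force:

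- **Adjustment is not free.** A reader might infer that it can never cost a full point. Step 5 does not support that: one cell averages just over 1 point and single trials can lose more. Separate two-arm models would cost more still (about 1.1 to 1.2 points for the markers with blocks), which is a reason to fit all four arms together.
- **The marker scale is open.** Section 4.1 says the trial will "remain powered to detect a mean difference of 20% (SD 30"%) just after citing rises relative to baseline, so percent change is a possible reading. Baseline would then already be in use and step 4 would not apply. Section 3.7.1 and Table 2 name no change score, so neither reading is certain.
- **The baseline draw is not fixed as pre-dose.** Table 1 places the draw, randomisation and supplementation all in Visit 1. Adjusting for a post-dose value could bias the comparison.
- **Missing baselines** can cancel a small gain (step 6).

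The last three are answered by conditions on the marker model. They do not affect the strata adjustment.

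**Conclusion.** The point holds as a cheap efficiency improvement. Using the strata is worth about 2 points of 1:1 power at R² 0.086 and about 4.5 at 0.20, with smaller gains for H1. Baseline adjustment of the markers is worth about 2 points at ρ = 0.3 and 9 at ρ = 0.5, on the 3-month-level reading. Every R² and ρ is assumed. The expected cost if the covariates predict nothing is about 1 point or less.

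Two stronger readings are not supported. One is that ignoring the strata makes the t-test invalid or inflates its error. In fact its size is at or below 0.20, and it falls to about 0.18 or 0.16 only if allocation is blocked, which Section 3.4 does not say, and the strata are prognostic to that degree. The other is that the trial is underpowered. In fact 21 per group gives 80.4% with the planned test.

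**What to change.** In Section 4.2.1 and Table 2:

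- Make the primary analysis one linear model per measure, with four-level arm, bone and fracture type. Test H1 to H3 as contrasts at alpha 0.20, with H1 the mean of the two high-dose arms minus low dose.
- For CTX and PINP, state whether the outcome is the 3-month level or the change from baseline, and add the baseline value of the same marker as a covariate in either case. With an absolute change, the treatment contrasts are the same as for the level.
- Use as baseline only samples drawn before the first dose. Keep participants with a missing baseline in the model, for example by mean imputation of the baseline.
- Keep the unadjusted t-test as a sensitivity analysis.
- State in Section 3.4 whether allocation is blocked within strata. Block sizes can stay in a restricted document.

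The cost is plan wording and minor programming, with no extra patients, visits or assays. The model spends 2 degrees of freedom (FIX-IT, RUST) or 3 (CTX, PINP) and assumes similar SDs across arms; the retained t-test gives a check that does not draw on arms outside the comparison.
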